To our knowledge, only one anti-scoliotic physical therapy intervention explicitly directed to patients with RTT was proposed in the literature.[35] This is a specific physical therapy regimen comprised of an intensive program of postural positioning and enhanced activity level carried out in cooperation with the participant's family members and caregivers (within the educational facility). The intervention was conducted with a 5-year-old girl with RTT whose Cobb's angle reduced from 30° to 20° over an 18-month treatment period through the use of positioning equipment, postural strategies (activating automatic equilibrium reactions, which oppose the natural scoliotic curve), and a motor activity program (walking or standing) during waking hours. This result was maintained for three years until the routine mentioned above ceased, when the child's scoliosis rapidly regressed. A recently published article from Romano et al. [36] replicated this intervention method with 20 participants with RTT in Italy and reported no change in scoliosis severity for this group of clients during a one-year follow-up. Thereby strengthening the validity of the approach proposed by Lotan, Merrick, and Carmeli.[35] Moreover, previous programs were found helpful in increasing the motor function of five girls with RTT in Ireland,[37] 17 girls and women with RTT in Italy,[38] and 40 individuals with RTT in northern Italy.[39] This accumulation of evidence provides initial evidence of the feasibility and acceptability of this type of treatment in a broad age range and a wide functional range of participants.

The intervention proposed in the current protocol is ecological and intensive in nature, will be carried out by primary caregivers within the participants' daily living environment (home and educational facility), and will be planned and supervised by therapists experienced in treating individuals with RTT. Moreover, the authors will remotely supervise the intervention by using an ad hoc developed smartphone application.

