## **Study Aim**

The current study aims to evaluate the effectiveness of an anti-scoliotic physiotherapy program carried out during daily life and focuses on hypercorrective postures and on increasing the level of activity to assess whether or not it is possible to slow the progression of scoliosis in girls with Rett syndrome (RTT).

The current research project has the following research objectives:

- Primary objectives:
  1. Build, implement and evaluate a physiotherapy program for contrasting scoliosis trajectory adapted to individuals with RTT;
  2. Develop a secondary deformity prevention program through early intervention for people with RTT.
- Secondary objectives:
  1. Build and evaluate the efficiency of a support application for carrying out rehabilitation exercises;
  2. Explore the factors influencing adherence and implementation of intervention from the perspective of both families and therapists in light of the above-mentioned application.

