## **Materials and Methods**

### **Study Design**

A randomized controlled study with a waiting list design will be applied.

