## **Sample Size and Power Calculation**

The information available in the literature suggests that the Cobb angle in RTT typically increases by approximately  $14 \pm 8^\circ$  Cobb per year. Based on these data, an alpha of 0.05 and a beta of 0.8, we estimate that for this study, the researchers will need a sample size including two groups of 10 subjects and that statistical significance will be achieved if both groups of participants will show an average increase in the scoliotic curve of less than  $12^\circ$  Cobb after the implementation of the proposed program.

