### **Statistical analysis**

The normality of each variable's distribution will be assessed using the Shapiro-Wilk normality test. The ages, amount of received physical rehabilitation interventions, scoliotic curve degrees, behavioral characteristics, and activity and gross motor functional levels obtained at T1 will be compared between the two groups to assess their comparability through Wilcoxon's signed-rank test or Student's T-test (dependent of the variable distribution characteristics). Changes that occurred in the variables of each group at T1, T2, and T3 will be evaluated with Friedman's test or with the repeated measure ANOVA (dependent on the variable distribution characteristics). Between groups comparison for each variable collected at T1, T2, and T3 and for their variations that occurred between T1 and T2 and between T2 and T3 will be conducted using the Wilcoxon's signed-rank test or Student's T-test (dependent of the variable distribution characteristics), applying an appropriate adjustment for the age and gross motor skills of the participants. Relations will be searched between variables collected at T1 and the changes in the scoliosis curve degree and motor functioning after the treatment using Spearman's rank correlation coefficient or Pearson's correlation coefficient (dependent on the variable distribution characteristics). Moreover, a relation between the compliance with the proposed program and the changes in the scoliosis curve degree and motor functioning after the treatment will be searched using the Spearman's rank correlation coefficient or Pearson's correlation coefficient (dependent on the variable distribution characteristics). The threshold for significance of the above-described analyses will be set at  $\alpha = 0.05$ . No correction for multiple comparisons will be applied.[48]

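### The within-group tests over T1, T2 and T3 cannot isolate the programme's effect, and the randomised T1-T2 comparison that can is not named as the efficacy test

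*Combined protocol and SAP*

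**What the plan says.** - **Aim (Study Aim):** "to assess whether or not it is possible to slow the progression of scoliosis in girls with Rett syndrome". This is a question about rate of progression, with treatment set against no treatment.
- **Design (Study Design):** "A randomized controlled study with a waiting list design will be applied". T1-T2 is the only period in which a treated group runs beside an untreated one. Under Study Protocol, Group 1 may keep using the application after T2, without the calls, while Group 2 starts the programme.
- **Within-group tests (Statistical analysis):** "Changes that occurred in the variables of each group at T1, T2, and T3 will be evaluated with" Friedman's test or repeated-measures ANOVA, depending on normality. There is no group-by-time term.
- **Between-group tests (next sentence of the same section):** "Between groups comparison for each variable collected at T1, T2, and T3 and for their variations that occurred between T1 and T2", and likewise between T2 and T3, by t-test or Wilcoxon signed-rank test, adjusted for age and gross motor skills.
- **Priority:** no analysis is named as primary. All share alpha 0.05, without multiplicity correction.
- **Success rule (Sample Size and Power Calculation):** both groups should average an increase below 12° after the programme. This too is a within-group criterion.
- **Missed visits:** no dropout rate and no missing-data rule is given.

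**The concern.** The null hypothesis of the within-group test is that the mean (or rank) is the same at all three visits. The protocol itself expects that to be false without treatment: the Introduction gives 14-21° per year, and the sample size section uses 14 ± 8° per year. Rejecting it therefore says that curves moved, not that the programme slowed them.

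One omnibus p-value also covers two different conditions. In Group 2 these are waiting and then programme; in Group 1 they are programme and then optional continuation with less support. The test cannot say which period produced the change.

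At stake is which p-value carries the conclusion. With no primary analysis and a within-group success rule, a within-group result can be presented as evidence of efficacy. The Background shows how this can happen: an earlier study without controls "reported no change in scoliosis severity for this group of clients during a one-year follow-up", and this is taken as support for the approach.

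**Working it through.** **1. The plan's own figure.** The plan gives no operating characteristics for the within-group tests. Its only calculation is 10 per group from 14 ± 8° per year, a 12° threshold, and "an alpha of 0.05 and a beta of 0.8". Read as a two-group comparison with 80% power, two-sided:

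n per group = 2 × [(1.960 + 0.842) × 8 / (14 − 12)]² = 2 × 125.6 ≈ 252.

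The stated 10 is not reproduced. That is a separate problem; n = 10 per group is taken as given below.

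**2. Inputs for the simulation.**
- Fast rate: 14 × 10/12 = 11.67° per 10-month period (sample size section).
- SD of change per period: 8°, or 8 × 10/12 = 6.67° if scaled in the same way. The documents do not say which applies.
- Slow rate, about 4° per period. The Introduction cites a cohort in which the square root of the Cobb angle rises by 0.438 per year. From an assumed 25°: (5 + 0.438 × 10/12)² − 25 = 5.365² − 25 ≈ 3.8°.
- Assumed: T1 Cobb uniform on 10-40° (the eligibility range); independent normal changes in the two periods.

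**3. Model.** Y(T2) = Y(T1) + D1 and Y(T3) = Y(T2) + D2, with D1 and D2 normal with the means below. One group of 10 girls, 3,000-4,000 runs per scenario, alpha 0.05.

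| Scenario, one group | RM-ANOVA significant | Friedman significant |
|---|---|---|
| Untreated, 11.67° in both periods (SD 6.7-8°) | about 100% | about 100% |
| Halved, 5.83° in both periods (SD 6.7-8°) | 86-95% | 71-86% |
| Untreated then halved, the Group 2 pattern (SD 6.7-8°) | 97-100% over both tests | same |
| Stopped, 0° in both periods (SD 6.7-8°) | about 4-7% over both tests | same |
| Untreated, 4° in both periods (SD 8°) | 57% | 43% |
| Halved, 2° in both periods (SD 8°) | 22% | 14% |

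Repeat runs differ by one or two percentage points.

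**4. Reading the table.** At the fast rate, a significant result is expected both with no effect and with a halving of progression. At the slow rate with SD 8°, an untreated group is non-significant in 100 − 57 = 43% (ANOVA) to 100 − 43 = 57% (Friedman) of runs, and could be mistaken for a stabilised one. A smaller SD would lower that share.

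**5. The contrast that does fit the question.** An unadjusted t-test on T1-T2 change, 10 per group, rejects in about 4-5% of runs with no effect, 33-46% if progression is halved, and 87-97% if it stops (SD 8° to 6.67°, fast rate). It has the right null, but limited power for partial slowing.

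**6. The success rule.** If the 12° threshold is read per 10-month period, the untreated expectation of 11.67° already lies below it. The section does not state the period.

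**7. Missed visits (secondary).** Friedman and classical repeated-measures ANOVA use complete rows. If a proportion d is missing independently at each of T2 and T3, 20(1 − d)² girls enter: 18.1, 16.2 and 12.8 for d = 5%, 10% and 20%. These rates are assumed.

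**The case against.** The strongest reply is that the plan already contains the right analysis. The sentence after the within-group tests compares T1-T2 change between the randomised groups, with adjustment for age and motor skills, and nothing gives the within-group tests an efficacy role. This stands: a reader who concluded that the plan has no analysis suited to its question would be wrong. It does not remove the point, because that contrast is not ranked above the others. Its adjustment omits the T1 Cobb angle, and the listed tests take no covariates; the signed-rank test is moreover a paired test.

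A reader might also infer that the within-group result comes out much the same whether or not the programme works. The figures do not support that in general. If progression stops, significance falls to about 4-7%. At the slow rate with SD 8°, halving takes it from 57% to 22% (ANOVA) or from 43% to 14% (Friedman). The similarity holds for partial slowing at the fast rate. In the other cases benefit appears as non-significance, which in 10 girls does not establish absence of progression and has no concurrent control behind it.

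Nor is the loss of girls with a missed visit the reason these tests miss the question. It is conditional on a dropout rate that the documents do not give; it would cost precision and might bias. The possible misreading of a non-significant result is likewise a risk, not something the plan commits to.

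**Conclusion.** The point holds in a limited form. The within-group Friedman or repeated-measures tests cannot isolate the programme's effect in either direction: significant in about 100% of untreated groups and 71-95% of groups with halved progression at 11.7° per period, and non-significant in about 43-57% of untreated groups at 4° per period with SD 8°. These figures rest on 10 girls per group, a uniform T1 distribution, independent normal changes, and the assumed rates and SDs.

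The defect is one of priority and specification. The randomised T1-T2 contrast is planned but not named as the efficacy test, not adjusted for T1 Cobb, and tied to tests that cannot carry the intended adjustment, while the written success rule is within-group. This should be corrected before analysis.

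**What to change.** 1. Name the between-group comparison of Cobb at T2 as the efficacy test. Analyse it by ANCOVA with T1 Cobb, age and T1 RESMES as covariates. A mixed model for T2 and T3 (same covariates, group, visit, group-by-visit, all available visits, small-sample degrees of freedom) is a reasonable alternative, with the group effect at T2 as the test.
2. Replace the within-group tests by mean changes per period with 95% confidence intervals, labelled descriptive.
3. If Group 2's T2-T3 change is compared with its own T1-T2 change, label it secondary and state that it assumes a stable natural rate of progression.
4. Reconcile the success rule in the sample size section with the named between-group test.

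Cost: SAP wording and a little more modelling; T1 Cobb and RESMES are already collected. In 20 girls, ANCOVA with three covariates leaves 20 − 5 = 15 residual degrees of freedom, against 20 − 2 = 18 for the unadjusted t-test. The change does not cure the limited power for partial slowing.

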## **Study Protocol**

The participants' parents will receive an information sheet regarding the study and informed consent for participation and collection of video materials at the recruitment. A reference telephone number and an e-mail address will be provided to be contacted in case they would like further information or would like to communicate the exit from the study. The eligibility of the candidates will be assessed at the time of recruitment (T1) through an initial neurological or physiatrist evaluation. At the same time, each participant will undergo a rehabilitation evaluation to collect the outcome measures (see section "Data collection") and create an individualized intervention plan specific to the participant's scoliosis, functional abilities, and parental/educational setting's availability. During the evaluation, the postural needs of the participants will also be identified, and a qualified technician will build or adjust the positioning devices, making them suitable for each intervention plan. Using block randomization, participating girls will be randomly divided into treatment (Group 1) or delayed treatment (Group 2) groups. Participants in Group 1 will begin carrying out the rehabilitation program immediately after the first assessment session (T1). Each program will require the daily performance of different postures and therapeutic activities at the girls' educational facilities and homes, based on the availability of families, for a duration of 10 months. Specific strategies that will be implemented will include maintaining asymmetrical postures that oppose the scoliosis curve during activities and exercises in sitting, standing, and walking positions (according to each participant's functional abilities). These strategies refer to a hypercorrective postural positioning of scoliosis. In addition, activities involving weight bearing on the lower limbs, such as walking and standing for at least two hours a day, will be encouraged, and passive stretching and spinal mobilization exercises will be conducted.

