### ***Scoliosis Progression***

The progression of scoliosis will be assessed during the study by measuring Cobb's angle on three anteroposterior X-rays of the spine collected respectively at T1, T2, and T3. The girl will be positioned in the most upright position comfortable for her. The angle will be measured using standard procedures. If the participant has an X-ray examination of the spine carried out in the manner prescribed for this study in the six months prior to the start of the intervention, this radiograph will be used as a pre-intervention examination. If the participant does not have an x-ray examination with the characteristics described above, it will be carried out as part of this project in compliance with the international guidelines for the management of scoliosis in RTT, which provide for the carrying out of six-monthly radiographic examinations in the presence of evolving scoliosis.[12] Moreover, the radiographic examinations carried out periodically by the participants before the recruitment at the participants' reference hospitals will be collected by the researchers to allow the extraction of data relating to the evolutionary trajectory of scoliosis up to the time of recruitment. The Cobb's angle will be obtained from the average value of three measurements carried out by independent blinded (to the treatment status of each subject) medical specialists with clinical experience concerning scoliosis in RTT. Using the results provided by different clinicians blinded to the procedure, the date of the x-ray is taken, and the functional state of each participant will allow a more reliable final measurement.[43]

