### ***Gross Motor Function Level***

The gross motor function level, including the ability to walk, will be measured during the rehabilitation assessments using the Rett Syndrome Motor Evaluation Scale (RESMES – Appendix 6). This scale includes 25 items that examine motor function divided into six sections: standing, sitting, postural transfers, walking, running, and climbing / descending stairs. Sixteen items are rated on a discrete scale, ranging from 0 (indicates no or very mild impairment) and 4 (severe impairment). Nine items related to walking skills are evaluated on a discrete scale with a score from 0 to 2 where 0 indicates that the activity could always be completed by the subject and 2 that is assigned if the item cannot be carried out. The items' scores are added together, thus giving a total RESMES score (range: 0 to 82). Moreover, a score for each section can be calculated. Additionally, the RESMES was designed to be completed by the primary caregivers of the person with RTT. Comparing the total score obtained by parents and doctors revealed a high correlation and no statistically significant difference.[44] This scale was recently validated on a sample of 60 girls and women with RTT (mean age: 12 years 5 months SD: 8 years 9 months; range: 3–40 years), showing optimal agreement between the assessors and strong internal consistency (reliability coefficient = 0.96 SD = 0.18; Cronbach's alpha coefficient for the full scale = 0.95 CI 0.93–0.97).[45]

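### In Group 1 the predictor correlations pair T1 Cobb and T1 RESMES with a change that contains the same T1 value, so measurement error biases them towards showing that girls with worse baselines do better

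*Combined protocol and SAP*

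**What the plan says.** Under Statistical analysis the plan states: "Relations will be searched between variables collected at T1 and the changes in the scoliosis curve degree and motor functioning after the treatment". The method is a plain correlation, "using Spearman's rank correlation coefficient or Pearson's correlation coefficient (dependent on the variable distribution characteristics"). The same section counts "scoliotic curve degrees, behavioral characteristics, and activity and gross motor functional levels obtained at T1" among the baseline measures, and the predictor search leaves none of them out.

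On significance: "The threshold for significance of the above-described analyses will be set at" 0.05, and "No correction for multiple comparisons will be applied". The adjustment for age and motor skills is attached to the between-group comparisons, not to these correlations.

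On timing, Study Protocol says: "Participants in Group 1 will begin carrying out the rehabilitation program immediately after the first assessment session (T1"). Group 2 is assessed again at T2 and treated from T2 to T3. The plan does not define change after treatment for each group, and does not say whether the groups are pooled for the correlations.

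On measurement, each Cobb value is the mean of three blinded readings of one film, for which "The girl will be positioned in the most upright position comfortable for her". The motor items are summed, "thus giving a total RESMES score (range: 0 to 82"), and a higher score is worse.

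**The concern.** A T1 film that reads high by chance gives a high baseline and, because T1 is subtracted, a small T2 minus T1 change. Averaging three readers reduces reading error, but not the error from how the girl happened to be positioned for that film. The result is a negative correlation between T1 Cobb and Group 1's Cobb change that has nothing to do with the programme. RESMES has the same coupling, and its bounds mean that a girl near either end can move in only one direction.

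Higher is worse on both measures, so the artefact looks like a better response in more severely affected girls. The Importance of the Research section hopes to learn what favours or limits effectiveness and to write guidelines from it. Baseline severity is an obvious candidate predictor, and its test is biased in a known direction.

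**Working it through.** The plan states no figure for these correlations, so there is none to reproduce.

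**Inputs**
- Baseline: T1 Cobb uniform over the eligible 10 to 40 degrees (assumption). True SD s_b = 30/√12 = 8.66.
- True 10-month change: SD s_c from 3 (assumption) to 6.7. The upper value scales the quoted 14 ± 8 degrees per year, reading ± 8 as an SD: 8 × 10/12 = 6.7.
- Film error, posture plus reading: SD s_e from 2 to 5 degrees (assumption; the documents give none).
- Test: Pearson, two-sided 0.05 (sidedness is not stated). Critical |r| is 0.632 at n=10 and 0.444 at n=20.

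**Group 1, true change unrelated to baseline**

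Expected r(T1, T2 − T1) = −s_e² / √[(s_b² + s_e²)(s_c² + 2s_e²)]

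| | s_e = 2 | s_e = 3 | s_e = 5 |
|---|---|---|---|
| s_c = 3 | −0.11 | −0.19 | −0.33 |
| s_c = 6.7 | −0.06 | −0.12 | −0.26 |

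For example, at s_c = 3 and s_e = 5: −25 / √(100 × 59) = −0.33.

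**Simulated two-sided false-positive rates** (40,000 trials per setting, nominal 5%)

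| How change is defined | n | Rate |
|---|---|---|
| Group 1 only, T2 − T1 | 10 | 5 to 14% |
| Group 2 only, T3 − T2 | 10 | 5%, mean r 0.00 |
| Group 1 T2 − T1 pooled with Group 2 T3 − T2 | 20 | 5 to 11% |
| All 20 changes taken from T1 | 20 | 6 to 28% |

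Nearly all of the excess is in the negative direction.

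**With the Introduction's natural history.** The yearly increase of 0.438 on the square-root scale makes larger curves progress more in degrees:
- From 10 degrees: (√10 + 0.438)² − 10 = 3.0 per year.
- From 40 degrees: (√40 + 0.438)² − 40 = 5.7 per year.

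This raises r. Group 1 mean r then runs from +0.05 (s_e = 2) to −0.23 (s_e = 5). At s_e = 3 it is about −0.04 to −0.06, and a significant negative r appears in about 3.0 to 3.5% of trials, against 2.5% nominal.

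**RESMES.** With no true change, r = −√[(1 − reliability)/2]. At the stated 0.96 this is −√(0.04/2) = −0.14. Variation in true change brings it nearer zero.

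**Alternative: T2 regressed on T1 in each randomised group.** Under the null, error shrinks both Cobb slopes by the same factor, s_b²/(s_b² + s_e²): 75/79 = 0.95 at s_e = 2 and 75/100 = 0.75 at s_e = 5. Simulated at 10 against 10, with and without the natural history, the mean slope difference was 0.00, the false-positive rate 4 to 5%, and the SD of the slope difference about 0.2 to 0.5.

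**The case against.** A reader might infer that measurement error alone will produce a finding that worse girls do better, or that the pattern would appear with no programme effect. The documents do not support that. The expected correlations lie well inside the critical values, at least 86% of Group 1 analyses would show nothing significant under the assumptions above, and the low end shows almost no inflation. The plan's own natural history offsets the artefact and at small error reverses its sign.

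Nor does the problem cover the whole sample. On the natural reading Group 2's change starts at T2, and the plan elsewhere names only the T1 to T2 and T2 to T3 intervals. The 6 to 28% range needs all 20 changes to start from T1. For Group 2 that means either its untreated period or a T1 to T3 change that the plan nowhere names.

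Three further points stand. The upper end rests on an assumed error SD of 5 degrees, although three blinded readers limit the reading part of it. The RESMES coupling is small at the stated reliability, and nothing shows girls clustering at 0 or 82. The search is exploratory, and the guideline ambition does not mention baseline severity.

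What survives is narrower. Group 1's same-variable correlations share the T1 error, nothing in the plan allows for it, and the offset from natural history is a second distortion rather than a cure. The 0.96 for RESMES is reported with internal consistency and may not capture test-retest error.

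**Conclusion.** The point holds as a bias in a secondary analysis, not as a predicted false result. For Cobb in Group 1 the expected distortion is about −0.06 to −0.33, with 5 to 14% false positives, if true change is unrelated to baseline. With the quoted natural history the mean correlation is +0.05 to −0.23. Sensible pooling with Group 2 gives about 5 to 11%. These figures rest on the assumed error SD, the uniform baseline, the true-change SDs and the Pearson branch. For RESMES the distortion is at most about −0.14 at the stated reliability.

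Whatever its sign, a raw correlation of T1 Cobb with Group 1's change mixes measurement error, natural history and programme effect. It cannot show which girls respond better. The efficacy comparison is not touched by this point.

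**What to change.** - Remove T1 Cobb with Cobb change, and T1 RESMES with RESMES change, from the correlation list.
- Instead, regress T2 on T1, group and group-by-T1 over T1 to T2 in both randomised groups. Report the slope difference as exploratory, with its confidence interval. For Cobb, shared error and natural history are common to both arms and cancel.
- For the correlations that remain, define the treatment change for each group and say whether the groups are pooled.

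This needs a few sentences and one regression per outcome, on data already planned. The costs are real:
- With a slope-difference SD of 0.2 to 0.5, a 95% interval spans roughly ±0.4 to ±1.0, so only strong effect modification would show.
- Group 2's treated period is not used.
- Error also shrinks any true slope difference, by the factor 0.75 to 0.95 above.
- For RESMES, floor or ceiling effects may not cancel fully if the programme shifts scores, so that result needs more caution.
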